## Secondary Outcome Measures\*\*

- 1) ECG and skin temperature confirmation
  - Confirm that ECG characteristics align with those from bench results using a simulator
  - Confirm that skin temperature readings align with those from bench results

\* Note that in the pathologic cohort of subjects, RR and rTV are NOT designed to be a primary method of validating the CPM System but are included in the data collection and analysis protocols.

\*\* Note that the secondary objectives and outcome measures only apply to the pathologic cohort of subjects and are NOT designed to be a primary method of validating the CPM System. These objectives and outcome measures are meant to gather more data in a controlled setting since the devices used to measure these specific parameters will already be used in the study.

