## Pathologic Cohort

The target population for this cohort is adult patients who have been diagnosed with cardiopulmonary conditions. These can include chronic pulmonary conditions, chronic cardiac conditions, and those who are taking diuretic medications, living with heart failure, Chronic Obstructive Pulmonary Disorder (COPD), or recovering from coronary-artery disease related events. The goal is to recruit a participant population with a range of body types and BMIs and an approximately even split of genders as well as conditions outlined above (e.g. at least 5 each of COPD, HF, recovering from a coronary artery disease related event, and taking diuretic medication).

The minimum sample size for this study is 20 subjects per cohort (40 participants total), who will all complete the entirety of exercises included in the respective cohort's study protocol.

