## Pathologic Cohort

Patients will be recruited and begin the study as they are identified and consent to the study. Recruiting will end when 20 patients have initiated the study. One participant will participate in the study at a time, with the duration of each of two visits lasting approximately one hour (the total commitment for any given participant being approximately 2 hours spread over the course of one day).

Upon arrival to the clinic on the day of the study visit, prior to the application of the reference and test devices, skin inspection of the application site will be conducted. The reference bioimpedance device will be placed on the participant and a reference measurement will be taken. These electrodes will be worn for the entire duration of the study, even between visits, in order to ensure placement consistency, although reference and test impedance measurements will never be taken concurrently and reference measurements will never be taken with the CPM Device on the participant to avoid device interference. The reference bioimpedance device

electrodes will be placed within 2 cm from the CPM Device's electrode placement on the left chest of the participant. After disconnecting the reference device from the electrodes, the CPM Device will then be applied to the participant's chest as described in the IFU materials supplied with the device (the study team will also have received training on the proper placement of the device prior to the initiation of the study). A skin marker will be used to mark around the device in order to later place it in the exact same location. On the CRF, the time that the CPM Device is placed on the chest for the first time will be denoted.

A Baseline measurement will then be taken using the CPM Mobile Application in order to assign a systemgenerated patient ID to the participant as well as to establish the tilt angle for the following measurements. The measurement should proceed with two positions; the first half of the measurement should be in a sitting-upright "Fowler" position, and the second half should be in a lying-flat "Supine" position.

In reference to the table below, subjects will be instrumented with the ADI device and laboratory-based reference impedance device along with a mouthpiece connected to a pneumotachometer and gas analyzer (only for the last three measurement items). In addition, they will be instrumented with an ECG for the indicated items.

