The exercises below will then be followed, with the time of the start of each exercise recorded in the CRF. Each exercise will last approximately 2 minutes, or the time that it takes to complete one full measurement with the CPM device in measurement mode (initiated by the CPM mobile app). Reference bioimpedance will be denoted at the beginning of each measurement in both a sitting and laying down position, following the CPM Device measurement flow. All CPM Device measurements include both a Fowler and a Supine portion.

Participants will be asked to breathe normally throughout the course of all measurements, including during the final three measurements which include the use of a device that tracks respiration rate and tidal volume. Reference devices to measure skin temperature and ECG will also be used during clinic visit two, before and after the CPM Device usage.

Subjects are to be instrumented with both the ADI device and reference impedance, mouthpiece, pneumotach, sampling line for O2 and CO2, ECG, and skin temperature.

Item	Description	Device/Mode	Duration	
1	Baseline reference TI measurement*	Bioimpedance reference	1 min	
2	Baseline measurement	CPM/Baseline Setup, App	3 min	
3	Reference TI measurement	Bioimpedance reference	1 min	
4	Application 1/Measurement 1**	CPM/Patient, App	2 min	
5	Application 1/Measurement 2	CPM/Patient, App	2 min	
6	Application 1/Measurement 3	CPM/Patient, App	2 min	
7	Reference TI measurement	Bioimpedance reference	1 min	
8	Application 2/Measurement 1	CPM/Patient, App	2 min	
9	Application 2/Measurement 2	CPM/Patient, App	2 min	
10	Application 2/Measurement 3	CPM/Patient, App	2 min	
t = 1 hour				
11	Reference skin temperature, ECG data	Reference temperature, ECG devices	1 min	

12	Reference TI measurement	Bioimpedance Reference	1 min
13	Application 3/Measurement 1; RR/TV	Reference spirometer, CPM/Patient,	2 min
	measurement	Арр	
14	Application 3/Measurement 2; RR/TV	Reference spirometer, CPM/Patient,	2 min
	measurement	Арр	
15	Application 3/Measurement 3; RR/TV	Reference spirometer, CPM/Patient,	2 min
	measurement	Арр	
16	Reference skin temperature, ECG data	Reference temperature, ECG devices	1 min

\* Measurements with the bioimpedance reference device refer to the length of time that it takes to get a stable thoracic impedance reading in both a sitting and lying down position.

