## Effectiveness and Endpoint Analyses:

Thoracic Impedance from the CPM System will be derived from the CPM analytics engine as described previously in the protocol, and the equivalent parameters will be recorded from the reference device output.

For pairs of measurements collected continuously with the CPM and reference device, scatter plots with the 45degree line of agreement superimposed will be constructed from paired observations from the two sources along with Bland-Altman plots of the data. The mean absolute error (MAE) and the root-mean-square error (RMSE) estimates of agreement will be calculated for each comparison, as well as correlation coefficients. The standard deviations of each of the agreement measures will also be computed. The R^2 value for the tidal volume measurement will also be calculated.

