# Endpoints

Thoracic Impedance Precision (primary)

- Std < 6 Ohms from measurement to measurement (short term) within a subject
- Std of Z to reference  $X \le 6$  Ohms for short- and long-term measurements
- Respiration Rate Accuracy (secondary)
- RMSE < 2 bpm between reference and test device
- *Tidal Volume Accuracy (secondary)* 
  - $R^2$  value > 0.5

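### The pathologic-cohort tidal-volume criterion R² > 0.5 rests on three normal-breathing readings per subject and names no unit, aggregation or sign, so the outcome depends on an unstated choice and each main reading can mislead

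*Combined protocol and SAP*

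**What the plan says.** In the protocol's Pathologic Cohort Data Analysis, the Endpoints list has an entry "Tidal Volume Accuracy (secondary") with the threshold R² > 0.5. The Effectiveness and Endpoint Analyses text for that cohort says only that an R² for tidal volume will be computed. Its description of the data is "For pairs of measurements collected continuously with the CPM and reference device", with no definition of a pair.

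The data come from Study Procedures, Pathologic Cohort. The mouthpiece and pneumotachometer are used "only for the last three measurement items", which are items 13 to 15 of the schedule, all within the third device application. The breathing instruction is: "Participants will be asked to breathe normally throughout the course of all measurements". The same sentence makes clear that this covers the three spirometer readings too. Each reading spans two positions: "All CPM Device measurements include both a Fowler and a Supine portion". On numbers, "The minimum sample size for this study is 20 subjects per cohort".

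Two other places bear on the meaning. Primary Outcome Measures describes the tidal-volume outcome as a within-subject correlation, and as correlation coefficients averaged across subjects. The note under Secondary Outcome Measures says that in this cohort "RR and rTV are NOT designed to be a primary method of validating the CPM System".

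**The concern.** Relative tidal volume is meant to follow change within a person. Testing that needs tidal volume to change, and here nothing makes it change: there are three consecutive readings at natural depth. The healthy cohort, by contrast, has exercises with shallow, natural, deep and very deep breaths.

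With so few points and so little imposed range, an R² threshold is sensitive to how it is computed, and the plan leaves that open. The same data could be called a pass or a fail according to a choice made after they are seen. This is the only numeric tidal-volume threshold set in the intended-use population, in a study meant to support a 510(k) submission.

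**Working it through.** **The plan's own figure.** No sample size, power or error rate is given for this criterion. The only calculation for the cohort concerns thoracic impedance: n = (5.1 × (1.96 + 1.65) / 6)² = 9.42, rounded up to 10. That reproduces the stated 10 but says nothing about tidal volume.

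**Inputs from the protocol.** 20 subjects; 3 readings each (60 in all); 2 positions per reading; threshold R² > 0.5, that is |r| > √0.5 = 0.707. The healthy-cohort sample-size text gives a worst-case error of 10%, and a respiration-rate error of 2.5% to 4% that it expects tidal volume to resemble.

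**Assumptions.** Readings are independent and normal within subject. The protocol gives no within-subject spread of tidal volume at normal breathing; 3%, 5% and 10% are assumed.

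**Reading A: per-subject R², or its mean.** With m pairs and no association, R² follows Beta(1/2, (m − 2)/2), with mean 1/(m − 1).
- m = 3 (one pair per reading): mean 1/2, equal to the threshold. P(R² > 0.5) = 1 − (2/π) × arcsin(√0.5) = 1 − (2/π)(π/4) = 0.50. If r must also be positive: 0.25.
- Mean of 20 such values above 0.5: 0.50 of 200,000 simulated trials. More than half of the 20 subjects above 0.5: 0.41.
- m = 6 (one pair per position): mean 1/5, P = 0.116 per subject. The mean over 20 subjects exceeded 0.5 in 0 of 200,000 trials.

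**Reading B: average signed within-subject r, three pairs, against 0.707.** With no signal, r has SD √0.5 = 0.707, so the mean of 20 has standard error 0.707/√20 = 0.158. The threshold lies 0.707/0.158 = 4.47 standard errors out, a probability of about 4 × 10⁻⁶ (0 of 200,000 simulated). Chance passes vanish.

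Now take a device with real signal: device value = true value + error, with spread s and error SD e. The true within-subject correlation is s/√(s² + e²). Simulated pass rates for 20 subjects × 3 readings:

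| Error e | Spread s | True correlation | Average r passes | Mean R² passes |
|---|---|---|---|---|
| 10% | 3% | 0.29 | 0.02% | 61% |
| 10% | 5% | 0.45 | 0.5% | 75% |
| 10% | 10% | 0.71 | 19% | 98% |
| 4% | 3% | 0.60 | 5% | 91% |
| 4% | 5% | 0.78 | 42% | >99% |
| 4% | 10% | 0.93 | 97% | about 100% |

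At a fixed error, the average-r result is driven by how much the subject's breathing happens to vary. In the mean-R² column, 61% to 98% at 10% error compares with 50% for a device with no signal.

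**Reading C: all 60 readings pooled.** With no signal of any kind, P(R² > 0.5) is 3 × 10⁻¹⁰ if readings are independent, and about 0.00025 at an assumed intraclass correlation of 0.95. But suppose the device separates large breathers from small ones and tracks nothing within a person. Assume a between-subject SD of 25% and a within-subject SD of 5% on both devices, with between-subject correlation 0.8. The pooled correlation is 0.8 × 0.25²/(0.25² + 0.05²) = 0.8 × 0.0625/0.065 = 0.77, so R² = 0.59. Simulated trials pass about 75% of the time. At a between-subject correlation of 0.75, R² = 0.52 and about 57% pass.

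**The case against.** A reader might infer that a device with no tidal-volume signal meets this criterion half the time. The documents do not support that as a general statement. The 50% belongs to a per-subject R² on one pair per reading, or to the mean of such values, and the plan prescribes neither. The one aggregation that the protocol names, in Primary Outcome Measures, averages correlation coefficients, and its chance pass rate is practically zero. Position-level pairs would also lower the per-subject figure to 0.12, and the reference to continuous collection may mean still more pairs.

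A reader might also infer that an inverse relation would count as a pass. That follows only from the literal R². The healthy-cohort endpoint justification equates the same threshold with R > 0.7, a positive correlation, although the pathologic-cohort justification does not repeat this. The planned scatter plots and correlation coefficients would show a negative relation.

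Finally, the protocol limits the weight of the result. Tidal volume here is secondary, is expressly not a primary validation, and is validated in healthy volunteers with imposed depth changes. No sample size or success rule depends on it.

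All of this stands, and it narrows the point. It does not rescue the criterion: adopting the averaged r exchanges a chance pass for a chance failure, and pooling answers a question about differences between people.

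**Conclusion.** The point holds in conditional form. The criterion has no defined unit, aggregation or sign, and three normal-breathing readings per subject cannot support a dependable threshold under the readings checked:
- Per-subject or mean R² on three pairs passes noise about 50% of the time.
- Average signed r almost never passes noise, but passes a device with the sponsor's assumed errors anywhere from 0.02% to 97% of the time, depending on breathing spread.
- Pooled R² can pass with no within-subject tracking, in about 75% of trials under the stated assumptions.

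The null results for three and six pairs are exact under independent normal readings. The other sizes depend on assumed spreads and between-subject correlations that the protocol does not give, and should be read as a range. Severity is minor to moderate, because the endpoint is secondary and the main tidal-volume validation is elsewhere.

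**What to change.** In the pathologic-cohort Endpoints list, remove R² > 0.5 as a pass/fail criterion for tidal volume and state that relative tidal volume is reported descriptively, in line with the note under Secondary Outcome Measures. In the matching analysis section, define a pair (per reading or per position) and name one summary before data are analysed: a signed within-subject (repeated-measures) correlation across all 20 subjects, with a confidence interval that treats the subject as the unit. Report the within-subject SD of reference tidal volume beside it, so that a low correlation caused by steady breathing can be recognised. Keep the tidal-volume criterion in the healthy cohort, where breathing depth is varied.

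The change is to wording only; no procedure, visit or sample size is affected. The sponsor gives up a secondary pass/fail statement in the intended-use population.

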# **Thoracic Impedance Endpoint Justification**

To determine the required precision for an impedance monitor to detect trends of worsening cardiopulmonary conditions, we looked into clinical standards. The ESC guidelines for the diagnosis and treatment of  $HF^1$  recommend that patients with an unexpected weight gain of >2kg in 3 days should increase their diuretic or alert their healthcare team. Using this as the guide for the change to be detected, we looked into the corresponding impedance change per kg of weight gain in patients with cardiopulmonary conditions. Gudmundsson *et al.* reported a change of 2.3 kg and 4.8 ohms (~2.1 ohms/kg) in the weeks preceding a major HF event. Note that those changes were reported using an implantable device which might be different from the thoracic impedance measured by the CPM system. Early data collected by the CPM project team show that an increase in 1kg corresponds to a 2.32 ohms decrease in the thoracic impedance. For the purpose of estimating the required precision, we will assume a 20hms/kg change.

If we define an event per the ESC guideline for weight changes, (>2kg/3days), and using the conversion factor above, we get a change of 4 ohms in 3 days. In order to estimate the precision needed for the CPM system, we assume an even slower change of 4 ohms in 5 days. In order to detect a change of 4 ohms over 5 days for a patient with a known baseline, the required precision is 6.1ohms. We will set the desired precision for the CPM system at 6ohms.

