## **Background** (*Include relevant experience, gaps in current knowledge, preliminary data, etc.*):

The Cardio-Pulmonary Management (CPM) System is intended for use in adults undergoing monitoring for cardiopulmonary conditions under the direction of a licensed medical professional to measure, record, and periodically transmit physiological data. One of the main challenges in managing these patients' care with the current standard of care lies in providing health care providers with insight on how patients are trending once diagnosed, and (post-discharge) identifying patients who are at high risk for an adverse event, so that these patients can be treated prior to being admitted or re-admitted to the hospital.

Studies such as MultiSENSE in 2017 have demonstrated, using a large cohort of patients implanted with a CRTD device, that it is possible to predict clinical decompensation (in this case, related to heart failure) using a combination of relevant parameters that include heart sounds, thoracic impedance, respiration, heart rate, and activity (Boehmer et al., 2017). Measurement and monitoring devices are important tools used to manage these at-risk populations; however, there are limited options that provide multi-parameter and noninvasive patient data collected and analyzed within one device.

[figure not shown]
The ADI At-Home CPM System acquires physiological data and derived measurements associated with the presence and progression of cardiopulmonary conditions, including S3 heart sound, respiratory rate and relative changes in tidal volume, changes in thoracic impedance, and electrocardiogram abnormalities. The end goal of the product is to collect, derive and transmit these measurements to the clinical care team daily and with high accuracy. These data enable the clinical care team to monitor their patients more closely, potentially resulting in more informed clinical management decisions and reducing the need for hospitalizations. This study aims to validate the accuracy of several of these parameters (respiration rate, relative tidal volume, and thoracic impedance) clinically, using both pathologic patients in the intended use population as well as healthy volunteers who will follow respiration patterns (changing rate and depth) mimicking those observed in patients with cardiopulmonary conditions.

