## Sample Size Justification:

Based on preliminary data, the standard deviation ( $\sigma$ ) of the thoracic impedance for an individual subject did not exceed 5.1  $\Omega$  when placement was controlled. Using the paired-difference equivalence test power formula, we calculate the number of subjects n needed to demonstrate that the 2 device measurements are equivalent ( $\delta = 0$ ) within 6  $\Omega$  (B = 6). To obtain a 2-sided alternative with 90% power we set  $z\alpha = 1.96$ , and  $z\beta = 1.65$ . We can then calculate the required n = 10. This suggests that with 10 subjects we would be able to demonstrate equivalence (with 90% power) if the differences in the measurements between CPM Device and the reference device are within 6  $\Omega$ . However, we know that our estimates of the standard deviation might be inaccurate since they are based on a small sample of data and did not include the same patient population. To account for that potential error, we plan to enroll 20 subjects.

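### Does the 6-ohm thoracic impedance limit have to change because the 6.1-ohm figure behind it cannot be reproduced?

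*Combined protocol and SAP*

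**What the plan says.** The Thoracic Impedance Endpoint Justification (pathologic cohort) starts from a guideline weight gain of 2 kg in 3 days and converts it at 2 ohm/kg to 4 ohm. It then stretches the period: "we assume an even slower change of 4 ohms in 5 days". The next step is "In order to detect a change of 4 ohms over 5 days for a patient with a known baseline, the required precision is 6.1ohms", followed by "We will set the desired precision for the CPM system at 6ohms".

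The pathologic-cohort Endpoints section uses 6 ohm twice as a primary limit. One is "Std < 6 Ohms from measurement to measurement (short term) within a subject". The other is the SD of the difference from the reference device, with the same 6 "Ohms for short- and long-term measurements". The Sample Size Justification for that cohort also uses 6 ohm as its equivalence bound ("B = 6). To obtain a 2-sided alternative with 90% power we set" the z values) and reports that the preliminary SD "of the thoracic impedance for an individual subject did not exceed 5.1" ohm.

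No reading schedule accompanies the 6.1-ohm figure. The nearest statement is in the Background: "The end goal of the product is to collect, derive and transmit these measurements to the clinical care team daily and with high accuracy". The Description of Investigational Device says that one short wear yields one measurement. The Intended Use refers only to periodic transmission.

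**The concern.** Each step as far as 4 ohm is shown, and then 6.1 ohm appears with nothing behind it. An SD larger than the change to be detected is surprising unless many readings are averaged. Daily use suggests about five readings in five days, and five readings at conventional error rates call for an SD well below 6.1 ohm.

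This passage is the only rationale for a number that decides both primary impedance endpoints, in a study meant to support a 510(k) submission. If the number were about twice too large, a device could pass and still miss most 4-ohm changes in an individual patient, while the report implied otherwise.

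**Working it through.** **Inputs from the documents.** Change 4 ohm; window 5 days; baseline known; limit 6 ohm (from 6.1); preliminary SD at most 5.1 ohm.

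**Assumptions, not in the documents.** One independent reading a day (5 in all); one- or two-sided 5% false-alarm rate; 80% or 90% power; precision means one SD.

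**Figures that reproduce.** Conversion: 4.8/2.3 = 2.09 ohm/kg, taken as 2; 2 kg × 2 ohm/kg = 4 ohm. Sample size: ((1.96 + 1.65) × 5.1/6)² = 9.42, rounded up to 10, as stated.

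**The 6.1-ohm figure.** No formula is given, so the usual one is tried: required SD = signal/(z for false alarms + z for power).

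- Sustained shift, 4 ohm present on all five days: signal = 4 × √5 = 8.944.
- Linear change of 0.8 ohm a day from the known baseline, days 1 to 5: signal = 0.8 × √(1 + 4 + 9 + 16 + 25) = 0.8 × √55 = 5.933.

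Readings needed for an SD of 6.1 ohm to suffice: sustained, (z sum × 6.1/4)² in total; linear, (z sum × 6.1)²/(0.64 × 55) per day. Both are rounded up.

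| Error rates | z sum | Required SD, sustained | Required SD, linear | Readings for 6.1, sustained (total) | Readings for 6.1, linear (per day) |
|---|---|---|---|---|---|
| One-sided 5%, 80% | 2.486 | 3.60 | 2.39 | 15 | 7 |
| One-sided 5%, 90% | 2.926 | 3.06 | 2.03 | 20 | 10 |
| Two-sided 5%, 80% | 2.802 | 3.19 | 2.12 | 19 | 9 |
| Two-sided 5%, 90% | 3.242 | 2.76 | 1.83 | 25 | 12 |

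No row gives 6.1 with five readings.

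**Detection when the SD is exactly 6 ohm, five readings.**

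- Sustained: 8.944/6 = 1.491. Φ(1.491 − 1.645) = 0.44 one-sided; Φ(1.491 − 1.960) = 0.32 two-sided.
- Linear: 5.933/6 = 0.989. Φ(0.989 − 1.645) = 0.26; Φ(0.989 − 1.960) = 0.17.

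These are values at the boundary. At the preliminary ceiling of 5.1 ohm, the sustained case is 8.944/5.1 = 1.754, giving Φ(0.109) = 0.54 one-sided and Φ(−0.206) = 0.42 two-sided.

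**Routes that do reach about 6.1 ohm.**

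- More readings: 20 over five days, sustained, one-sided 5%, 90% power: 4 × √20/2.926 = 6.11.
- Looser error rates: five readings, sustained, SD 6.1, one-sided 10%: Φ(8.944/6.1 − 1.282) = Φ(0.185) = 0.57 detection.
- Precision meaning two SDs: five readings, sustained, one-sided 5%, 90% power: SD = 8.944/2.926 = 3.056, and 2 × 3.056 = 6.11.

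The documents do not say which of these, if any, was used.

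**The case for a change.** The strongest case for a change is that the gap needs no assumption to establish. The number is decisive, nothing on the page yields it, and only the sponsor can supply the inputs. Under the use that the documents suggest, it falls short even on terms that favour it: a known baseline, independent readings and the full shift on every day. Stretching the event from 3 to 5 days does not add caution either. With daily readings and a sustained shift (one-sided 5%, 80% power), it loosens the required SD from 4 × √3/2.486 = 2.79 to 3.60 ohm. If the two-SD route was the real one, 6 ohm was carried into the Endpoints section as an SD about twice as large as the one derived.

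The omission stands. The shortfall does not, because it depends on inputs that the plan never adopted. Daily transmission is described as a product goal, not as an input to this calculation. No document sets a detection rate for impedance in one patient, and the Background describes a system that combines several parameters. The error rates in the Sample Size Justification concern the number of subjects needed for device equivalence, a different question. The two-SD reading is conjecture, and the Endpoints section, which lists an SD under the heading of precision, points away from it. Also, both pathologic-cohort sessions take place within one day, so the SD measured here does not translate directly into five-day detection in either direction.

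**Conclusion.** The 6.1-ohm figure is undocumented, but it is not shown to be wrong. The apparent gap (2.8-3.6 ohm sustained, 1.8-2.4 ohm linear, against 6) rests on one independent reading a day, 5% false alarms, 80-90% power and precision meaning one SD. The plan fixes none of the first three and does not define the fourth.

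The possible responses explain why no change follows:

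- Writing out the derivation would be good documentation, but would leave the endpoints, analyses and pass/fail rule as they are.
- Keeping 6 ohm and rewording its rationale has the same effect.
- Lowering the limit would have real consequences and no agreed basis. A limit of 3.6 ohm or less would lie below the preliminary SD of up to 5.1 ohm, to satisfy a detection standard that the plan does not set.

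Analysts can compute both SDs and compare them with 6 ohm as written, and the Intended Use claims no detection of a 4-ohm change. What remains is a caution for reporting. A pass at 6 ohm shows measurement precision within that limit. It does not by itself show that a 4-ohm change over 5 days would be detected; for a device exactly at the limit, on the assumptions above, detection would be 32-44% (sustained) or 17-26% (linear).
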